3.1.3 Data collection

Information on exposures (depression status, and treatment), outcome (PTD & LBW), and other psychiatric disorders (comorbidity) will be ascertained through KPNC EMR data sources for all

88,000 women who have been screened for peripartum depression. Confounders not available from the KPNC EMR will be ascertained during interview of the stage-two subsample of 3,600 women (Figure 2). OBGYNS will inform all pregnant women who screen positive by PHQ-9 about our study during their prenatal visits. Table 1 describes briefly the sources and categories of factors to be ascertained.

		Universal Screening	EMR data	Interview
Depression and treatment	Depression and its severity	X	X	
	Psychotherapies	X	X	
	Antidepressant use	X	X	
	Combination therapy	X	X	
	Other psychiatric disorders		X	
Outcome	Gestational Age/PTD, LBW		X	
Potential confounders, mediators and effect modifiers	Risk factors for PTD, LBW		X	X
	History of mental illness		X	X
	Reproductive history		X	X
	Preexisting diabetes or GDM		X	X
	BMI		X	X
	History of depression	X	X	X
	Substance abuse		X	X
	Reproductive and pregnancy history		X	X
	Family and social support		X	X
	Demographic characteristics		X	X
Family history of mental illness			X	

Depression status and severity

Depression status and its severity during pregnancy will be ascertained through PHQ-9 scores from the universal depression screening and clinical diagnosis. All pregnant women who come to the first prenatal visit will be screened for depression using the PHQ-9, which has been validated in many studies as an instrument for screening for depression with high sensitivity (> 88%) and specificity (> 88%) in obstetric patients¹⁰³⁻¹⁰⁷. PHQ-9 was chosen as the screening instrument after consultation with many nationally recognized experts in the field of diagnosis and treatment of peripartum depression balancing out many factors including scientific validity and feasibility for a large scale population-based screening program. As a currently accepted cutoff, PHQ-9 scores (≥ 10) in combination with evaluation by medical practitioners will be used to determine whether a pregnant woman screens positive for depression. A score above 10 will be used as a measure of the severity of depression. Women who screen positive are referred by clinicians, under the screening protocol, to departments of

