Outcomes (PTD & LBW): Gestational age at delivery is determined by obstetricians based on multiple sources including ultrasound dating, physical examination, and LMP. Birthweight is measured by medical practitioners at delivery. This information is recorded in the KPNC EMR. In several studies conducted by the PI, more than 99% of participants had reliable information on gestational age and birthweight at delivery in the KPNC EMR. For the remaining <1% that may have delivered outside KPNC hospitals, we are also able to obtain information through searching various databases including outside payment service databases. In addition, KPNC has a well-established Neonatal Minimum Data Set which verifies all NICU admissions for diagnosis and treatments. This database allows ascertainment of information on gestational age and birthweight for deliveries with missing information. We will also ascertain other related information such as indications for PTD and other pregnancy or labor complications for further classification of PTD. A sample of PTD and LBW records will be selected and verified by manual review of medical records for quality control.

Potential confounders. In the stage-two subsample, we will conduct a structured telephone interview to ascertain detailed information on potential confounders that may not be available from the KPNC EMR. The focus will be known and suspected risk factors for PTD and LBW, personal and family history of mental illness, demographic, reproductive and psychosocial factors (e.g., social and family support that may be related to depression, PTD, and LBW), BMI, diseases during the index pregnancy (e.g., GDM), diet, lifetime and prenatal smoking. The PI and his research team have extensive experience ascertaining information on these variables for many of his previous NIH-funded studies. Questionnaires with these questions have been used in many previous

studies. Based on our experience conducting telephone interviews with KPNC pregnant women, a response rate of 80-85% is expected.

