4.1.3 Populations

Stage I population

All KPNC women aged 18 years (legally allowed to participate in these types of studies at KPNC) or older who are pregnant and who participate in the universal peripartum depression screening will be eligible for the study. We expect that about 88,000 pregnant women will be

eligible during the study recruitment period. If a woman becomes pregnant a second time during the study period (an unlikely event given the short recruitment period of less than three years) and she was already in the study for her previous pregnancy, her second pregnancy will not be included in the study so as to avoid non-independent observations.

All participants in the universal depression screening will be identified and information on screening results, referrals, treatments, pregnancy related conditions and outcomes will be collected through linkage to various data sources of our comprehensive EMR system.

Stage II samples

A sample of 400 pregnant women from each of the nine cohorts previously described will be randomly selected to form Stage II samples. The random selection will be spread evenly throughout the study period so that all of the estimated 88,000 participants in Stage I will have an equal chance of being selected. They will be selected after their inclusion in Stage I with known status of depression and treatment, mostly before the 3rd trimester to avoid interviewing after delivery to reduce participation and recall biases. Any change in exposure status (depression and treatment) after initial assignment will be rectified and finalized during analyses, as we have done in other similar studies with two-stage design (with different exposures in pregnancy).

Participants in Stage II samples will be interviewed to obtain more detailed information on depression and its treatments. The Stage II samples will also allow for direct ascertainment of compliance with prescribed medications. Studies based on pharmacy data alone usually have to make an assumption of 100% compliance with dispensed medications. In this study, we can directly examine the compliance and assess its potential impact on treatment effectiveness. This will be an important strength for this study.

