Through the interview, we will also directly ascertain compliance to prescribed medications for treating depression. We will make appropriate adjustment for compliance ratio in data analysis to more accurately estimate the treatment effectiveness after taking into account of non-compliance. In addition, we will also ascertain additional confounders including multivitamin intake during pregnancy and physical activity.

Informed consent will be obtained before the interview. All contact procedures will follow the standard contact and recruitment procedures as required by KPNC's IRB. Based on our experience with similar studies among KPNC pregnant women, a participation rate of 70-75% among eligible pregnant women can be expected. The recruitment will continue until 400 subjects from each of the nine cohort groups have completed the interview.

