Point and interval estimates of the relative hazard of PTD associated with each treatment modality (A, B, C), relative to no treatment (D) will be calculated via semiparametric maximum likelihood estimates of Cox proportional hazards regression parameters, with adjustment for potential confounders, as described above. In determining potential confounders in our regression models, we will first examine risk factors that may be plausibly linked to depression and PTD. Inclusion of potential confounding factors in our final regression models will be evaluated based on comparison of adjusted and unadjusted relative hazard ratios⁷⁹. Departures from model assumptions will be assessed via diagnostic plots of weighted residuals and tests for interaction between exposure and time (gestational age). The assessment of confounding variables for inclusion in regression models and testing of model assumptions will be performed in the stage-two sample using standard software for fitting Cox regression models. After determining the appropriate set of confounders and that there are no departures from model assumptions, the stage-one information on primary exposure and outcome will be incorporated using the semiparametric maximum likelihood estimator. This process applies to analyses of the remaining aims.

These comparisons will allow us to assess possible treatment effects on reducing PTD through both pharmacotherapy and psychotherapy. When compared to untreated (Cohort D), the comparison will be made after controlling for underlying severity of depression as measured by PHQ-9 scores or clinical diagnosis of severity before treatment. Table 2 shows that depression severity is relatively comparable among comparison groups, allowing control for confounding by indication (underlying depression severity, a unique strength of the proposed study due to the availability of PHQ-9 scores through the universal depression screening).

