6.1.1 Propensity Score Analysis

In addition to the conventional analyses outlined above, we will apply a propensity score (PS) analysis method to reduce or correct for any selection bias into treatment groups in our conventional approach described above. PS analysis uses information about all measured covariates to balance unobserved factors between treatment groups. It is not necessary to know the exact relationship of unobservable factors with measured covariates - as long as there is any type of relationship between unobservable and measured factors, propensity score analysis can reduce over 90% of selection bias associated with unobserved factors⁸⁰. Given the study aims, which primarily focus on various pair-wise comparisons of treatment groups, PS analyses will be

conducted in the cohort subsets consisting of each pair of groups of interest. This will allow us to construct a multivariable logistic model for dichotomous outcomes to calculate a propensity score, i.e., the probability of receiving a given treatment, vs. another treatment (or no treatment), as a function of all known factors that might affect the treatment outcome. This model will include the same variables used in our conventional Cox proportional hazards/logistic regression models described above. The resulting probabilities (propensity scores) will be used to analyze the extent of overlap on all covariates, using graphical methods and frequency distributions. Areas of non-overlap in score between treatment groups will be trimmed (removed) from analyses. Stratified Cox proportional hazards models, with stratification on deciles of propensity score, will be used to compare the two treatment groups with respect to PTD risk^{81, 82}. Logistic regression analyses of low birthweight will include the categorized score as a covariate. We will compare results from our conventional regression models with results from the PS analysis. We note that results with adjustment for confounding via propensity score techniques are not expected to appreciably differ from results using traditional regression adjustment^{81, 83}. If we find that results differ, we will report the PS analysis results as our main findings due to the correction for selection bias in our measured characteristics.

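### Covariate selection has no timing condition, so factors that arise or change after treatment starts can enter the regression and propensity models and remove part of the total treatment effect

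*Combined protocol and SAP*

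**What the plan says.** **Candidates.** Section 3.1.3, in the paragraph on potential confounders, includes "diseases during the index pregnancy (e.g., GDM), diet, lifetime and prenatal smoking". Section 4.1.3 adds "additional confounders including multivitamin intake during pregnancy and physical activity". Table 1 places GDM, BMI, substance abuse and social support in one block labelled "Potential confounders, mediators and effect modifiers" and gives no row a specific role.

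**Interview timing.** Of the stage-two women, Section 4.1.3 says "They will be selected after their inclusion in Stage I with known status of depression and treatment", mostly before the third trimester.

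**Selection.** Section 6.1 (Aim 1) has two steps. First, "we will first examine risk factors that may be plausibly linked to depression and PTD". Then, "Inclusion of potential confounding factors in our final regression models will be evaluated based on comparison of adjusted and unadjusted relative hazard ratios". No numerical cut is given. The step is run on the interviewed women: "The assessment of confounding variables for inclusion in regression models and testing of model assumptions will be performed in the stage-two sample". The same process carries over to the other aims. Depression severity is the only covariate tied to a time before treatment.

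**Propensity score.** Section 6.1.1 says "This model will include the same variables used in our conventional Cox proportional hazards/logistic regression models described above". If the two approaches disagree, the propensity results become the main findings.

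Nothing in the document limits covariates to pre-treatment values, says how mediators are handled, or states whether a total or a direct effect is the target.

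**The concern.** Aim 1 asks whether treated women have lower fetal risk than untreated women, and Aim 2 asks which treatment does better. Section 5 wants benefit weighed against side-effect risk. Together these describe a total effect. If treatment changes a complication or a behaviour, and that in turn changes the risk of PTD or low birthweight, the path is part of the effect being sought. Adjusting for it takes that part out, and can also open a path through unmeasured common causes of the complication and the outcome.

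The propensity analysis is no safeguard. It uses the same variables, so agreement between the two analyses would not reveal the problem. Aim 3 is exposed in the same way, because these factors may lie between untreated depression and the outcome.

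**Working it through.** **1. The plan's yardstick.** Inputs from Section 6.2.2: 400 per group, PTD rate 8% to 11%, two-sided 0.05, 80% power. Taking the rate as the reference-group rate, expected events are 400 × rate × (1 + HR). The Freedman condition is √events × (HR − 1)/(HR + 1) = 1.960 + 0.842 = 2.802.
- 8%: HR = 1.834 (stated 1.83).
- 11%: HR = 1.693 (stated 1.69).
- With 1,600 per group: 1.382 and 1.322 (stated 1.38 and 1.32).

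The stated figures reproduce, and the concern does not alter them.

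**2. Why the rule cannot separate the roles.** Let a binary factor have prevalence m0 in the untreated and m1 in the treated, and multiply PTD risk by g. Then

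unadjusted ratio ÷ adjusted ratio = (1 + m1(g − 1)) / (1 + m0(g − 1)).

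No term records whether the factor came before or after treatment. A confounder and a mediator with the same m0, m1 and g give the same change.

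**3. Illustrative size for a complication that treatment makes more common.** The documents give no values for m0, m1 or g, so all are assumed.
- 7% to 10%, g = 1.5: 1.05/1.035 = 1.01.
- 6% to 9%, g = 3: 1.18/1.12 = 1.05.
- 8% to 14%, g = 3: 1.28/1.16 = 1.10.

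On the log scale, 1.05 is about 16% to 19% of the two-stage detectable effect (0.052/0.322 to 0.052/0.278), and 1.10 is about 31% to 35% (0.098/0.322 to 0.098/0.278).

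**4. Illustrative share removed, and chance of being kept, when treatment makes the factor less common.** The direct ratio is assumed to be 0.80, and total = 0.80 × (1 + m1(g − 1))/(1 + m0(g − 1)). The share of the log effect removed is 1 − ln(0.80)/ln(total). The chance of being kept comes from a simulation of 400 per group and 3,000 runs, with a Mantel-Haenszel risk ratio standing in for the hazard ratio. The 10% and 5% cuts are also assumptions.

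| m0 | m1 | g | Total | Log effect removed | Kept, 10% cut | Kept, 5% cut |
|---|---|---|---|---|---|---|
| 8% | 6% | 1.5 | 0.79 | 4% | not run | not run |
| 10% | 6% | 2.0 | 0.77 | 14% | 4.5% | 28% |
| 25% | 15% | 2.0 | 0.74 | 27% | 36% | 79% |
| 30% | 15% | 2.5 | 0.68 | 43% | 89% | 99% |

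The adjusted ratio exceeds the total by a factor of 1.01 (0.80/0.792) in the first row and 1.18 (0.80/0.676) in the last.

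**5. Direction.** In the table, adjustment hides benefit. If treatment has a direct ratio of 0.80 but raises a complication from 8% to 14% with g = 3, the total is 0.80 × 1.10 = 0.88. Adjusting reports 0.80 and so hides harm.

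**6. Which values can post-date treatment.** Screening takes place at the first prenatal visit and again at the glucola visit, at 22-24 weeks (Section 3.1.3). For a woman treated after the first screen, GDM found at or after the glucola visit can follow treatment. For a woman who first screens positive at the glucola visit, earlier smoking or an existing complication precedes treatment and may be a true confounder. The same variable can therefore play either role, depending on its date.

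**The case against.** The strongest reply is that change in the hazard ratio is not the sole criterion. A subject-matter screen comes first, the second step is worded for confounding factors, and Table 1 names mediators as a separate role. This stands as far as it goes, and a reader who inferred that the hazard-ratio comparison is the only rule would be wrong. But the screen has no timing condition, Section 3.1.3 itself files index-pregnancy diseases under confounders, and no analysis section says what is done with a mediator.

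A second reply is that weak mediators would rarely be kept. At an assumed 10% cut, the factors 1.01 and 1.05 in step 3 would not be expected to qualify, and 1.10 is borderline (1 − 1/1.103 = 9.4%). This also stands, although the plan sets no cut. A reader might infer that the rule will select mediators; the documents show only that it can, and they contain no evidence that treatment alters GDM, diet or smoking here.

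Third, a late interview does not make every item a post-treatment one. Family history, demographics and smoking before pregnancy refer to earlier periods. The questionnaire is not in the documents, so its reference periods are unknown.

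Fourth, a reader might conclude that all index-pregnancy conditions should be excluded. That would discard true confounders for women first positive at 22-24 weeks. Nor does a date set by positive screen or treatment exist for Cohort E, which has neither.

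**Conclusion.** The point holds as a gap in the selection rule. Factors that can follow treatment are candidate confounders, both selection steps ignore timing, and the same set feeds a propensity score that may supply the main findings. The plan can therefore condition on mediators and estimate something other than the total effect that Aims 1 and 2 and Section 5 call for.

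The size and direction cannot be computed from the documents. The complication scenarios give factors of 1.01 to 1.10; commoner or stronger mediators give more, up to 1.18 and 43% of the log effect in the table. Every input is an assumption. The documents do not support saying that the treatment effect will be adjusted away, that all interview items are affected, or that the bias runs one way. The point merits correction because the remedy is cheap and the planned comparison of methods would not expose the problem.

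**What to change.** - State that the total effect of treatment is the target for Aims 1 and 2.
- Name the main regression and propensity sets in advance, and limit both to covariate values dated before treatment start. Use a matching index date in Cohort D (such as first positive screen or diagnosis) and a comparable gestational-age date in Cohort E for Aim 3.
- Date each covariate instead of dropping it by name, so that GDM or smoking that precedes treatment stays in.
- Word interview items on changeable behaviours and social support for the period before the index date.
- Use values after the index date only in a labelled sensitivity or mediation analysis.
- Specify the time-dependent dose and timing analyses of Section 6.1 separately. A condition arising in pregnancy can precede and influence later treatment there, so baseline-only adjustment is not plainly right.

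The cost is SAP wording, date filters on EMR variables and some interview wording. No added recruitment is needed and the stated detectable effects do not change. The downside is that some early conditions recorded late, and some behaviours that cannot be dated precisely, would be left out of the main model, with some loss of confounding control.

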4 STUDY DURATION, ENROLLMENT AND SITES

The proposed study will be completed within three years and will involve eligible patients from all Kaiser Permanente Northern California facilities. Start-up will occur during the first three months and will involve obtaining IRB approval, hiring staff, training, conducting focus group interviews, testing data collection materials, developing and revising interview instruments (including the questionnaire) for stage-two data collection of information on confounders, establishing mechanisms for identification of eligible subjects through the EMR. Data collection (including data linkage, establishment of depression screening registry, recruitment and conducting interviews) will be ongoing from month 4 through month 27. Ascertainment of diagnosis and treatment of depression and pregnancy outcomes will continue from month 10 through month 31. Data cleaning and analysis as well as report writing will be carried out during the last 6 months. The timeline for activities involved in the study is as follows:

Months 1-3	Obtain IRB approval. Hire staff. Train interviewers. Set-up tracking database. Develop algorithm for identifying eligible participants. Create interview instruments including questionnaire and instructions, operations manual, and pilot test questionnaire. Conduct focus group interviews.
Months 4-27	Identify and include eligible pregnant women for the stage-one sample. Conduct data linkage and build the peripartum depression screening registry . Classify 88,000 women from stage-one sample into treatment categories based on their depression status and treatment regimens. Select a random sample of 400 from each category to form the stage-two subsample. Conduct telephone interviews with stage-two subsamples.
Months 10-31	Ascertain outcomes of interest.
Months 30-35	Clean data, conduct and complete data analyses, and prepare final report.
Months 35-36	Create materials for dissemination of the findings. Dissemination of the findings, which will continue beyond month 36.

4.1 Study Population

4.1.1 Inclusion Criteria

- 1) Females \geq age 18
- 2) Kaiser members
- 3) Pregnant beyond 20 weeks of gestation during the recruitment period
- 4) Meeting the definition of one of the following nine cohorts:

Cohort A (depression only): pregnant women who are depressed and use only antidepressants

Cohort A (depression with comorbidity): pregnant women who are depressed and use only antidepressants

Cohort B (depression only): pregnant women who are depressed and receive psychotherapy only

Cohort B (depression with comorbidity): pregnant women who are depressed and receive psychotherapy only

Cohort C (depression only): pregnant women who are depressed and receive antidepressants and psychotherapy

Cohort C (depression with comorbidity): pregnant women who are depressed and receive antidepressants and psychotherapy

Cohort D (depression only): pregnant women who are depressed and receive no treatment

Cohort D (depression with comorbidity): pregnant women who are depressed and receive no treatment

Cohort E: pregnant women who are not depressed (screen negative) and receive no treatment

